Aim 3 (A3). Evaluate the impact of the staff intervention on resident falls, accidents and injuries and on quality of life using a prospective experimental design that derives information from five sources: (1) resident interviews (2) staff informants (3) observational data (4) chart and (5) incident/accident report data.

Primary Hypothesis: The frequency of falls, accidents and injuries will decrease in the

intervention group, relative to the comparison group after implementation of the training intervention.

Secondary Hypotheses: 1. Resident quality-of-life as measured by affective state will improve in the intervention group, relative to the comparison group after implementation of the training intervention.

2. Resident behavior problems will decline in the intervention group, relative to the comparison group after implementation of the training intervention. Resident behaviors will mediate the relationship between the intervention and the falls/accidents/injuries outcome.

Trial design

This is a pragmatic, prospective, cluster randomized trial (facility level) design with three waves of data collection (baseline, 6- and 12-months) at 12 assisted living facilities in two New York regions. There will be three levels of clustering: facilities within regions, units within facilities and repeated measures on residents within units, with the regions fixed. On a rolling basis, six facilities will be selected at random and recruited in New York City and the nearby suburban counties (downstate region). Six facilities in the upstate New York region of Rochester will also be randomly selected. Three facilities in each region will be randomized to usual care or to the intervention on a 1:1 ratio. Facilities allocated to the usual care group will receive the intervention after completion of their 12 month data collection.

Methods: Participants, interventions and outcomes

Study setting

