$\eta = \log(p_{ijk} / (1 - p_{ijk})) = \beta_0 + \beta_1 X_{ijk} + FU_{jk}$, where FU_{jk} is a random effect associated with facility and unit.

The formula for the sample size per group using the method of Diggle is:

$m^* = (z_{\alpha} \sqrt{2PQ} + z_{\beta} \sqrt{p_0 q_0 + p_1 q_1})^2 (1 + (n-1)\rho) / (n(p_1 - p_0)^2)$; and using the GEE method:

$m^* = \frac{(Z_{1-\alpha/2} + Z_{1-\beta})^2 (\pi_1 p_0 (1 - p_0) + \pi_0 p_1 (1 - p_1)) (1 + (n-1)\rho)}{2n\pi_0\pi_1(p_0 - p_1)^2}$. The formula below is adjusted with variance inflation factor (V_{if}) and reliability(R_{el}): $m = V_{if}m^* / R_{el}$ and

$$V_{if} = (1 + (n_e - 1)\rho_e)(1 + (n_s - 1)\rho_s n_e p_e / (1 + (n_e - 1)\rho_e))$$

where $n_s = 5$ is the average number of units in the facility, $\rho_s = 0.015$ is the ICC for facility, $n_e = 17$ is the average number of residents in the unit, $\rho_e = 0.03$ is the ICC for unit, and the reliability:

$$R_{el} = 0.95.$$

The following table assumes $\alpha = 0.05$, power $(1 - \beta) = 80\%$, $R = 0.95$ and $V_{if} = 2.5$ (With $n_e = 17$,

$ICC_{Unit} = 0.03$, $N_s = 5$, $ICC_{Facility} = 0.015$, the fall rate at follow-up: $p_0 = 33\%$ and $p_1 = 20.75\%$). Two

scenarios for ρ (the average correlation of the outcomes over waves) were posited:

Group	Fall rate P(y=1)				Diggle Method		GEE Method	
	Baseline Rate	6 Month	12 Month	Combined 6M & 12M	M ($\rho = 0.5$)	M ($\rho = 0.6$)	M ($\rho = 0.5$)	M ($\rho = 0.6$)
Intervention	37%	22%	19.5%	20.75%	404	431	399	425
Usual Care	37%	34%	32%	33%	404	431	399	425

As shown, with 525 per group, power is adequate for intent-to-treat (ITT) analyses, including all respondents. Because randomization is at the facility rather than individual level, there is the potential for imbalance on baseline variables and missing covariate data. Assuming attrition of

15% at wave 1, it is estimated that 445 per group will have at least baseline and one additional wave of data included, using the EM missing data algorithm; thus, power is adequate to detect the posited difference in fall reduction of about 12% even with attrition.

Recruitment

All residents are approached and invited to participate. For those who do not wish to be interviewed, a different or the same interviewer approaches again at another time that may be more amenable to the resident. All resident questions are addressed and interviews occur at a time and place preferred by the resident.

Assignment of interventions: allocation

Sequence generation

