Based on our experience in the conduct of many studies with residents in long term care facilities, we expect 15% attrition at 6 months and up to 40% at 12 months follow up, mainly related to discharge, hospitalizations and death. These percentages have been considered in the power calculations. All enrolled individuals who still reside at the facility at the follow-up visits will be invited to participate at follow-up at a convenient time for the respondent. Multiple attempts will be made to interview these residents.

Data management

Data entry and quality: All screening and evaluation data will be collected using a computer assisted personal interview (CAPI) system. This method provides accuracy in data collection, because the system does not accept out-of-range values, and does not allow for deviation from prescribed skip patterns. The DCC will create scoring and cleaning programs for scales within instruments. Although the CAPI and data entry systems should not allow these types of errors, the cleaning programs serve to double check the accuracy of the data. Periodically, the data manager will review all data for duplicate records, illogical collection dates or times of interview, outlier and out of range values, and illogical contingencies using program syntax created for each data file. After any corrections are made, items distributions will be reviewed to make sure no anomalies remain. In addition, the project coordinator periodically reviews entire files as a quality assurance measure.

Data storage, data safety and security: All laptops used for data collection and office based desktop computers are password protected and Bitlocker encrypted. Laptops will not leave the facility. Laptops with encrypted data are stored in a locked cabinet at the facility and not removed until study end. They are dedicated to the project and not connected to the internet. Log sheets will also be kept in a locked onsite storage area.

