Analyses for the primary hypothesis for the distal outcome: The primary analyses will examine, on an ITT basis, the differences between the usual care and intervention groups in the reduction of falls/accidents/injuries over time. Other approaches, e.g., the analysis of the “as treated” sample can result in biased estimates of the causal treatment effect due to compromised random assignment. Our primary approach to analyses is guided by our own experience,⁵⁷ and reviews.^{58,59} Depending on the level of missing data, analytic strategies (see below) can be used to address non-compliance, e.g.⁶⁰ Based on prior trials that we have coordinated, sampled from this population, 1 year attrition is between 30% and 40%; thus for 6-month data (projected attrition of 15%), the ITT analyses of all subjects will be feasible. Longitudinal analyses will include those with at least baseline and one follow-up. Sensitivity analysis will be performed using multiple imputation under different assumptions for missing data.

Because randomization is at the facility rather than individual level, imbalance may be observed on baseline variables. Preliminary analyses will be performed to determine whether the groups are balanced. Two-tailed tests of significance will be performed. Binomial tests are to be conducted on dichotomous variables, Poisson tests on nonbinomial (e.g., count) data, and *t* tests on ordinal data, adjusting standard errors for clustered data within facilities; *p* values are reported because the design does not permit randomization at the level of the individual.

Effect on likelihood of falls/injuries/accident reduction:

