Adverse event reporting and harms

All adverse events (AEs) and severe adverse events (SAEs) will be reported by the interviewers to the Project Manager who will update the Adverse Events Reporting Form and alert the PI.

Given that the study intervention is staff training, and there are no physical components to the participant evaluation (e.g., no blood draws or physical examinations), it is expected that no AE or SAEs will be related to study participation. Given that this is an older study population, SAEs (e.g., hospitalizations, death) are expected to occur, with no relationship to study participation.

Thus, per the NIA sample SAE/AE Process flow diagram, these events are not unexpected and will be reported to the DSMB at annual teleconferences. However, in the unlikely event that an AE or SAE is determined to be definitely, probably, or possibly related to the study it will be reported as follows: SAEs will be reported by the PI to the DSMB, NIA, and IRB within 24 hours of the event being reported to the Investigator; AEs will be similarly reported within two weeks of the event. Although there will be multiple assisted living facilities enrolled, it is unlikely that these participating sites will have their own IRBs; thus, there will not be site specific IRB notification beyond that to the Weill Cornell Medical Center and the Hebrew Home at Riverdale IRBs.

Plans for communicating important protocol amendments to relevant parties (e.g. trial participants, ethical committees)

Any protocol amendments will be presented first to the DSMB for approval. If approved, plans will

be presented to the IRB.

Dissemination plans

Study outcomes will be presented in manuscripts in relevant peer-reviewed journals and at scientific meetings. Depending on the wishes of the facility administrators, there may be a meeting for participating facilities staff to present study findings.

Abbreviations

AEs: adverse events

ALRs: assisted living residences

BRDS: Behavior Recognition and Documentation Sheet

CAPI: computer assisted personal interview

CAREDIAG: Care Dementia Diagnostic Scale

DCC: data coordinating centre

DSMB: Data Safety and Monitoring Board

FTQ: Feeling Tone Questionnaire

HTE: heterogeneity of treatment effects

INCARE: Institutional Comprehensive Assessment and Referral Evaluation

IRB: Institutional Review Board

ITT: intent-to-treat

LTSS: long-term services and support

MEMs: mixed effects models

NIA: National Institute on Aging

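### Deaths and hospitalisations are presumed unrelated in advance and never compared by arm, so an excess or a reduction in trained facilities could go unrecognised

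*Combined protocol and SAP*

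**What the plan says.** All places are in the combined protocol and SAP.

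- **Adverse event reporting and harms.** Interviewers report every AE and SAE to the Project Manager, who updates the reporting form and alerts the PI. The section expects no event to be related to participation, and adds that "SAEs (e.g., hospitalizations, death) are expected to occur, with no relationship to study participation". Such events go to the DSMB at annual teleconferences. An event judged related, at any level from definite to possible, goes to the DSMB, NIA and IRB within 24 hours (SAE) or two weeks (AE). The section does not say who makes that judgement or by what criteria.
- **Objectives, Aim 3.** The primary hypothesis opens "The frequency of falls, accidents and injuries will decrease in the" and names the intervention group.
- **Statistical methods.** "Two-tailed tests of significance will be performed". Falls/accidents/injuries, affect, depression and behaviour are compared between arms. Deaths, hospitalisations and SAEs are not mentioned.
- **Plans to promote participant retention.** "we expect 15% attrition at 6 months and up to 40% at 12 months follow up, mainly related to discharge, hospitalizations and death".
- **Concealment mechanism; Who will be blinded.** The biostatistician, the trainer (who informs the facilities) and one principal investigator know the assignment. Interviewers, field managers and project managers are not told it.
- **Data monitoring committee; Interim analyses.** The DSMB reviews risk versus benefit, retention and site performance. No section says that it sees data by arm. No interim analysis or stopping guideline is planned.

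**The concern.** Judging relatedness event by event suits a treatment whose effect can be recognised in one patient. Here the treatment acts on staff, and through them on everyone in the facility. If training changed deaths or admissions, the change would show mainly as a difference in rates between trained and untrained facilities. A blinded reporter looking at one death has little basis for calling it related, and the plan tells that reporter in advance to expect that it is not.

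The plan also pulls in two directions. Its primary hypothesis is that training changes the frequency of resident injuries. Its harms section expects no adverse event to be related to the study, although an injury, or an admission after one, may be exactly what the training is meant to affect.

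At stake is what the trial can say about harm. A fall benefit accompanied by more deaths or admissions might look like a clean benefit, and a real fall in admissions might be missed.

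**Working it through.** **1. The plan's own figures.** The Sample size section gives 17 residents per unit, unit ICC 0.03, 5 units per facility, facility ICC 0.015, reliability 0.95, and fall rates of 33% v 20.75%.

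- V_if = (1 + 16 × 0.03) × (1 + 4 × 0.015 × 17 / 1.48) = 2.50, as stated. This omits the trailing p_e in the printed formula; reading p_e as the unit ICC gives 1.51, which does not match.
- Diggle formula, two waves, ρ = 0.5, two-sided 0.05, 80% power: m* = 153.3, so m = 153.3 × 2.5 / 0.95 = 403.4 (stated 404). At ρ = 0.6, m = 430.3 (stated 431).
- GEE formula: 398.0 and 424.5 (stated 399 and 425).
- One-sided versions give 313 to 339 and do not match. The two-tailed statement stands beside the baseline checks, but the sample size is two-sided as well.

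The plan gives no figure for deaths, hospitalisations or SAEs. What follows is illustrative.

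**2. A range of risks (assumption).** One-year attrition of 30% to 40% is 0.30 × 1,050 = 315 to 0.40 × 1,050 = 420 residents. The documents do not split it by cause. If one- to two-thirds of exits were death or hospitalisation, that is 105 to 280 residents, or 10% to 27%. This only sets a range to calculate over. It is not a hospitalisation risk, because residents who return from hospital are not exits.

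**3. Precision if the arms are equal.** 525 per arm, 12 facilities, 12 − 2 = 10 df, t = 2.228, V = 2.5 (assumed to carry over from falls). Half-width = 2.228 × √(2p(1 − p)V / 525).

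| Risk p | V = 2.5 | V = 1 (no clustering) |
|---|---|---|
| 10% | 6.5 points | 4.1 |
| 20% | 8.7 | 5.5 |
| 27% | 9.7 | 6.1 |

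**4. Power.** Noncentral t, two-sided 5%, 10 df, SE = √([p₀(1 − p₀) + p₁(1 − p₁)] × 2.5 / 525).

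| Usual care v intervention | SE | Noncentrality | Power |
|---|---|---|---|
| 10% v 15% | 0.0322 | 1.55 | 29% |
| 20% v 30% | 0.0420 | 2.38 | 58% |
| 10% v 20% | 0.0345 | 2.90 | 74% |
| 20% v 35% | 0.0430 | 3.49 | 88% |

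Only a large excess (for example 105 v about 184 of 525 residents, the last row) would be detected reliably. A 1.5-fold excess would often be missed.

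**5. Does another section already cover it?** The falls/accidents/injuries analysis is by arm, but it does not count deaths or other admissions. It also needs at least one post-baseline observation, so residents who die or leave before 6 months may not contribute. The comparison of completers with those lost to follow-up is not described as by arm. SAEs pooled over arms cannot show an excess in one arm.

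**The case against.** The strongest reply is that oversight is better than the quoted sentence suggests. The harms section states an expectation and then gives a route for events judged possibly related. Event Logs, staff documentation sheets and incident reports record circumstances, so an injury during a staff-managed incident could be linked to the training. Every SAE reaches an independent DSMB with a safety officer and a biostatistician, and with a duty to weigh risk against benefit and review site performance. The most direct harm pathway, injury, is already compared by arm. The plan calls the intervention minimal risk. The DSMB also reviews monitoring plans that may contain more than this document shows.

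Much of that stands, and it rules out stronger readings. A reader might infer that harm can show only as a difference between arms, that any excess would certainly be reported as zero related events, or that the safety conclusion is fixed before data exist. The documents support none of these: the possibly-related route exists, and no section says that the safety statement will be the count of related events.

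A reader might also infer that the trial already holds a complete randomised comparison and discards it. That is not shown either. Follow-up visits invite only residents still living in the facility, and no section describes ascertainment after discharge.

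What the reply does not supply is a by-arm comparison of deaths and hospitalisations, or any statement that the DSMB receives one.

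**Conclusion.** The concern holds as a gap with a better method available, not as a demonstrated safety failure. The plan presumes these events unrelated, judges relatedness singly through a largely blinded chain, and plans no by-arm comparison. A difference in either direction could go unrecognised, and the existing safeguards cover this only partly.

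The added comparison would be imprecise, with half-widths of about 6.5 to 9.7 points, and it could not exclude important harm. It would still give an interval where the plan now gives none. These figures rest on assumed risks of 10% to 27%, on a V_if borrowed from falls, and on all 525 residents per arm contributing. The true clustering of deaths and admissions is unknown. It is worth correcting, and it does not threaten the primary analysis.

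**What to change.** 1. **Adverse event reporting and harms:** keep individual relatedness only as the trigger for expedited reports. Remove the advance presumption of no relationship as a basis for any conclusion on harm.
2. **DSMB reports:** at the annual calls already planned, have the biostatistician who knows the allocation supply deaths and hospitalisations by arm, with residents and resident-months at risk.
3. **Statistical methods:** add an all-cause comparison by arm of deaths and, separately, of hospitalisations recorded while enrolled and resident, whatever the judged relatedness. Allow for facility clustering with small-sample df, and report the difference with a 95% CI. Describe it as estimation, not proof of safety.

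Deaths and hospitalisations are preferable to total AE counts because they depend less on staff recognition, which the training is meant to raise.

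The cost is protocol and SAP wording, one table per DSMB call, and a short additional analysis of events the plan already has interviewers report. The fields on the AE form are not listed, so check that dates and hospitalisations are captured alike in both arms. Downsides: the DSMB sees safety counts by arm, the interval is wide, and events after a resident leaves the facility may be incomplete and should be reported as such.
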